#### **4.11.3. Supplementary Analyses**

Supplementary analyses for the Phase 3 portion of this study are included to demonstrate robustness of analyses methods using different censoring rules, missing data imputations, populations, and analyses assumptions. Supplementary analyses for selected outcomes have been previously described and include the following:

- Analyses of key endpoints using the mFAS (Section 4.2.1)
- Analyses of the primary endpoint using the PPS (Section 4.2.1)
- Hybrid imputation approach with NRI and MI for categorical variables, and mLOCF and MI for continuous variables (Section 4.4.4)
- Tipping point analysis (Section 4.4.6)

#### **4.11.4. Dosing Evaluation Analyses**

Additional analyses will be conducted within the following subgroups of the FAS population for the treatment dosing evaluation.

- SALT baseline severity subgroups: severe (SALT score of 50%-94%) and very severe (SALT score of 95%-100%)

- Duration of current AA episode at Baseline subgroups:  $< 4$  years and  $\geq 4$  years.

The dosing analyses will be evaluated on the following endpoints:

- SALT  $\leq 20$  at Week 36;
- ClinRO Measure for EB Hair Loss score of 0 or 1 with  $\geq 2$ -point improvement from Baseline at Week 36 (among patients with ClinRO Measure for EB Hair Loss  $\geq 2$  at Baseline);
- ClinRO Measure for EL Hair Loss score of 0 or 1 with  $\geq 2$ -point improvement from Baseline at Week 36 (among patients with ClinRO Measure for EL Hair Loss  $\geq 2$  at Baseline);
- SALT change and percent change from baseline through Week 36.

The statistical analyses will follow the analysis methods for Phase 3 portion specified in Section 4.2.3. For the categorical endpoints, the odds ratio with CI and corresponding p-value from the logistic regression model, percentages, difference in percentages, and CIs of the difference in percentages using the Newcombe-Wilson method without continuity correction will be reported. For the continuous endpoints, ANCOVA will be used. For the analyses performed on the subgroups defined by the duration of current AA episode at Baseline ( $< 4$  years or  $\geq 4$  years), the covariate of duration of current episode at Baseline will not be included in the model.

#### **4.11.5. Analysis Beyond Week 36 Placebo-controlled Period**

Statistical analysis beyond the Week 36 Placebo-controlled period will be used to support the long-term efficacy and safety assessment of the treatment. Since the long-term extension and bridging extension periods are not placebo-controlled, only descriptive statistics will be provided unless otherwise stated. Table JAHO.4.8 summarizes the analyses planned beyond Week 36. Further details will be specified in a future version of the SAP.

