To compare the maintenance of efficacy for patients randomized to remain on baricitinib, compared with patients randomized to placebo at Week 52 of the long-term extension period, as measured by physician-assessed signs of AA	
 
• Proportion of patients maintaining SALT <math>\leq 20</math> at Weeks 64, 76, 88, 104, 120, 136, 152, 168, 184, and 200
 
• Proportion of patients experiencing a loss of treatment benefit (<math>>20</math>-point absolute
 

	
worsening in SALT score) at Weeks 64, 76, 88, 104, 120, 136, 152, 168, 184, and 200.
 
 
Time to loss of treatment benefit (>20-point absolute worsening in SALT score)
 

For patients experiencing loss of treatment benefit after randomization to placebo at Week 52:
 
 
To evaluate the recapture of efficacy for patients who were retreated after experiencing a loss of treatment benefit during the long-term maintenance period as measured by physician-assessed signs of AA
 
To evaluate the recapture of efficacy for patients who were retreated after experiencing a loss of treatment benefit during the long-term maintenance period as assessed by PRO and quality of life tools
 
	
 
Proportion of patients that achieve a SALT <math>\leq 20</math> at 12, 16, 24, and 36 weeks of retreatment with baricitinib
 
Percent change in SALT score at 12, 16, 24, and 36 weeks of retreatment with baricitinib
 
Proportion of patients with a PRO for Scalp Hair Assessment score of 0 or 1 at 12, 16, 24, and 36 weeks of retreatment with baricitinib
 

Abbreviations: AA = alopecia areata; ClinRO = clinician-reported outcome; EB = eyebrow; EL = eyelash; HADS = Hospital Anxiety and Depression Scale; PRO = patient-reported outcome; SALT = Severity of Alopecia Tool; SALT50 = at least 50% improvement from Baseline in SALT score; SALT75 = at least 75% improvement from Baseline in SALT score; SALT90 = at least 90% improvement from Baseline in SALT score; SALT100 = 100% improvement from Baseline in SALT score.

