### 3.1.2. Study Design

[figure not shown]
The study design includes 5 periods: a 5-week screening period; a 36-week double-blind placebo-controlled treatment period; a 68-week long-term extension period; a 96-week bridging extension; and a posttreatment follow-up period. The Schedule of Activities (SOA) will be the same for patients randomized during Stage 1 and Stage 2, except that some patients randomized during Stage 1 might have one or more unscheduled visits after the Decision Point.

- **Period 1:** Screening period (Visit 1) is between 3 and 35 days prior to Visit 2 (Week 0).
- **Period 2:** 36-week double-blind, placebo-controlled treatment period is from Week 0 (Baseline; Visit 2) to Week 36 (Visit 8).
- **Period 3:** 68-week, long-term extension period with randomized withdrawal (for responders) is from Week 36 (Visit 8) to Week 104 (Visit 18).
- **Period 4:** Bridging extension period is from Week 104 (Visit 18) and up to Week 200 (Visit 24)/Week 248 (Visit 26). Subjects who have completed Week 104 and have not

met criteria of permanent discontinuation will have the possibility to remain in the trial for up to 96/144 additional weeks (up to Week 200/248).

- **Period 5:** posttreatment follow-up period; the posttreatment follow-up visit should occur approximately 4 weeks after the last dose of investigational product (IP). Patients who have completed Week 200/248 and who will continue on marketed product beyond Week 200 do not need to complete Period 5 (Visit 801).

Note: Patients who have discontinued IP and remain in the study for more than 28 day without IP will have an Early Termination Visit (ETV); however, a separate follow-up visit (V801) is not required. [Figure JAHO.3.2](#) illustrates the study design. The full visit schedule is outlined in the protocol.

Abbreviations: ClinRO = clinician-reported outcome; EC = exclusion criterion; eGFR = estimated glomerular filtration rate; ET = early termination; IP = investigational product; PBO = placebo; PTFU = posttreatment follow-up; QD = once daily administration; RW = randomized withdrawal 1; SALT = Severity of Alopecia Tool; V = Visit.

Note: Subjects who have completed Week 104 in the Long-term extension and have not met criteria of permanent discontinuation will have the possibility to remain in the trial for up to 96/144 additional weeks (up to Week 200/248) and have similar follow-up procedures.

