a Applicable to all patients at time of screening See EC [9] in protocol for treatments that will require washout.

b The maximal baricitinib dose for patients with renal impairment (defined as eGFR <60 mL/min/1.73 m^2) will be 2-mg QD (see Protocol).

- c At Week 36 patients in the placebo treatment arm who have NOT achieved SALT  $\leq 20$  will be rescued and re-randomized in a 1:1 ratio to baricitinib 2-mg or baricitinib 4-mg. All patients in the baricitinib treatment arms will continue in their current treatment arm regardless of treatment response at Week 36. Patients in the placebo arm who have achieved a SALT  $\leq 20$  will remain on placebo at Week 36. These patients who have experienced spontaneous regrowth on the scalp will remain on placebo for the remainder of the trial, even if relapse is observed later during the study.
- d At Week 52, responders (SALT  $\leq 20$ ) who are eligible (i.e., stayed on the same dose of baricitinib from initial randomization at Visit 2) will be randomized in a 3:1 ratio to either stay on their current dose of baricitinib or transition to placebo (randomized withdrawal).
- e Patients who have been in the baricitinib 4-mg treatment group from Baseline and who have never achieved a SALT  $\leq 20$  by Week 52 AND do not have a  $\geq 2$  point improvement in ClinRO Measure for Eyebrow or Eyelash Hair Loss (nonresponders) at Week 52 will be automatically transitioned to placebo. See footnote “f” for discontinuation criteria at Week 76.
- f Patients who are nonresponders (a SALT  $> 20$ ) at Weeks 52 AND 76 will be automatically discontinued from the study at Week 76, unless they have a  $\geq 2$ -point improvement from baseline in ClinRO Measure for Eyebrow or Eyelash Hair Loss. See Protocol for more details.
- g Responders who experience a loss of treatment benefit after Week 52 ( $> 20$ -point absolute worsening in SALT score) who were randomized to placebo at Week 52 (randomized withdrawal) will be retreated with their baricitinib dose, as randomized at Baseline (Visit 2). Patients who were randomized to remain on baricitinib (randomized withdrawal) will continue to receive the same dose of baricitinib. See Protocol for more details.

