Patients who achieve a SALT  $\leq 20$  at Week 52 (responders) AND who have remained on the same dose of baricitinib from randomization (Visit 2) to Week 52, will enter the randomized withdrawal, which is meant to evaluate the change in clinical response after treatment withdrawal, and does not account for whether the sample size is sufficient to detect statistical difference between baricitinib and placebo. It is expected that there would be approximately 100 patients eligible for the randomized withdrawal.

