### 4.2.1. Analysis Populations

**Table JAHO.4.1. Analysis Populations**

Population	Description
Phase 2, Week 12 Interim Analysis Set (IAS)	The first approximately 100 randomized and treated patients in Phase 2 portion within Stage 1 who completed Visit 5 (Week 12) assessment or discontinued early. Patients will be analyzed according to the IP to which they were randomized at Baseline (Visit 2).
Phase 2, Week 36 Interim Analysis Set (IAS)	The first approximately 100 randomized and treated patients in Phase 2 portion who completed Visit 8 (Week 36) assessment or discontinued early. Patients will be analyzed according to the IP to which they were randomized at Baseline (Visit 2).
Full Analysis Set (FAS)	All patients enrolled in Phase 3 portion, and who are randomized to baricitinib 4-mg, baricitinib 2-mg, and placebo treatment arms in both Stages 1 and 2 will be included in the FAS. Patients will be analyzed according to the IP to which they were randomized at Baseline (Visit 2).
Modified Full Analysis Set (mFAS) Population	All patients enrolled in Phase 3 portion, and who are randomized to baricitinib 4-mg, baricitinib 2-mg, and placebo treatment arms in both Stages 1 and 2, and received at least 1 dose of IP, will be included in the mFAS. It excludes patients with female pattern baldness and male patients with diffuse AGA a (Grade IV and above) (Norwood 1975) identified at Week 36. Patients will be analyzed according to the IP to which they were randomized at Baseline (Visit 2).
Per-Protocol Set (PPS)	The PPS will include all mFAS patients who are not deemed noncompliant with treatment, who do not have any of the important protocol deviations that exclude patients from the PPS, and whose investigator site does not have significant GCP deviations that require a report to regulatory agencies. The important protocol deviations, including the subset that result in exclusion from the PPS, will be determined while the study team remains blinded, prior to the primary outcome database lock.
Randomized Withdrawal Population	All patients who enter the randomized withdrawal with non-missing SALT score at Week 52 will be included in the Randomized Withdrawal Population. They will be analyzed according to the IP to which they were randomized at Week 52.

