Fisher's exact test will be used to test for differences between baricitinib and placebo group for AEs, discontinuations, and other categorical safety data. Continuous vital signs, body weight, and other continuous safety variables, including laboratory variables, will be analyzed using an ANCOVA with treatment and baseline value in the model. The significance of within-treatment group changes from baseline will be evaluated by testing whether or not the treatment group LSM changes from baseline are different from zero; the standard error for the LSM change will also be displayed. Differences in LSM will be displayed, with the p-value associated with the LSM comparison to placebo or appropriate comparator and a 95% CI on the LSM difference will also be provided. In addition to the LSMs for each group, the within-group p-value for the change from baseline will be displayed.

Due to the COVID-19 pandemic, some visits may have been conducted remotely. In order to evaluate the impact of remote visits on the clinical trial, sites were required to record the visit method (e.g., onsite visit, virtual visit, etc.) for visits beginning 1 March 2020. For data collected at the unscheduled postbaseline visit that falls within the visit window, the visit method should be considered the same as recorded for the scheduled visit for this window. If the visit method is a telephone interview or a virtual visit, the visit is considered remote. However, if the visit method is missing for the scheduled visit, but central lab was collected and/or vital assessments are available, then it will be considered an onsite visit, otherwise it will be considered a remote visit.

For F-DBL the analyses for the efficacy and safety will be only descriptive statistics provided to both categorical and continuous endpoints. No statistical inferential test will be provided, unless stated otherwise.

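### The SAP restricts the randomized-withdrawal comparison to descriptive statistics for lack of placebo control, but that comparison is itself randomised against placebo and needs a planned between-arm estimate with its uncertainty

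*SAP*

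**What the plan says.** SAP 4.11.5 covers everything after the Week 36 placebo-controlled period: "Since the long-term extension and bridging extension periods are not placebo-controlled, only descriptive statistics will be provided unless otherwise stated". It gives no other reason.

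The randomized withdrawal falls inside that span. SAP 3.1.2 describes Period 3 as a "68-week, long-term extension period with randomized withdrawal (for responders) is from Week 36 (Visit 8) to Week 104 (Visit 18". A figure footnote in the same section says that eligible Week 52 responders "will be randomized in a 3:1 ratio to either stay on their current dose of baricitinib or transition to placebo". Table JAHO.4.1 says of this population: "They will be analyzed according to the IP to which they were randomized at Week 52". The objective in Table JAHO.2.1 begins: "To compare the maintenance of efficacy for patients randomized to remain on baricitinib, compared with patients randomized to placebo at Week 52". That table lists it as other secondary and outside multiplicity control.

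For the methods, Table JAHO.4.8 lists descriptive summaries of maintained SALT ≤20 and of worsening by more than 20 points, and a Kaplan-Meier plot for time to worsening. Tables JAHO.4.9 to 4.15 add further descriptive or Kaplan-Meier rows.

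SAP 4.2.3 has a general log-rank rule for time-to-event data, with an optional Cox model. It also discusses covariates in models for the withdrawal population. For the final database lock the same section says: "No statistical inferential test will be provided, unless stated otherwise".

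**The concern.** The stated reason fits patients outside the withdrawal, who have no concurrent randomised placebo group after Week 36. It does not fit the withdrawal arms, which do.

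The objective asks for a comparison, and the tables deliver two sets of one-arm summaries. In the SAP supplied, this is the only randomised evidence on what happens when responders stop treatment. Without a pre-specified contrast, the choice of effect measure, dose grouping and interval method is left until after results are available. Readers would have to form the difference and its uncertainty themselves.

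**Working it through.** **Reason set against design**

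| Element | SAP location | Content |
|---|---|---|
| Reason for description only | 4.11.5 | Extension periods lack placebo control |
| Design | 3.1.2 | 3:1 randomisation, current dose v placebo, at Week 52 |
| Grouping for analysis | Table JAHO.4.1 | As randomised at Week 52 |
| Objective | Table JAHO.2.1 | Compare those two arms |
| Planned output | Tables JAHO.4.8 to 4.15 | Descriptive or Kaplan-Meier; no contrast |

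The first row is contradicted by the second, and the last row does not meet the objective.

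**The plan's own number.** SAP 4.1 states: "It is expected that there would be approximately 100 patients eligible for the randomized withdrawal". It shows no derivation, so only a plausibility check is possible.
- 625 Phase 3 patients at 2:2:3 (SAP 4.1) give about 179 placebo, 179 on 2 mg and 267 on 4 mg.
- Planning response rates, taken as if they held at Week 52: 0.30 × 267 = 80.1 and 0.20 × 179 = 35.8, total 115.9.
- With assumed attrition of 10% to 15%: 115.9 × 0.90 = 104 and 115.9 × 0.85 = 99.

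The figure is plausible. At 3:1 it gives about 75 v 25.

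**Precision of a pooled contrast.** The documents give no maintenance rates, so those below are illustrative. The method is Newcombe-Wilson without continuity correction, already named in SAP 4.2.3. With Wilson limits (l, u) for each proportion p:

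lower = (p1 − p2) − √[(p1 − l1)² + (u2 − p2)²]
upper = (p1 − p2) + √[(u1 − p1)² + (p2 − l2)²]

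- 60/75 (80%; Wilson 69.6 to 87.5) v 13/25 (52%; 33.5 to 70.0): difference 28. Lower = 28 − √(10.4² + 18.0²) = 7. Upper = 28 + √(7.5² + 18.5²) = 48.
- 60/75 v 15/25 (60%; 40.7 to 76.6): difference 20. Lower = 20 − √(10.4² + 16.6²) = 0.4. Upper = 20 + √(7.5² + 19.3²) = 41.

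**Precision within dose.** The 4-mg share of expected responders is 80.1/115.9 = 69%. Of 100 patients, about 70 come from 4 mg (52 v 18) and 30 from 2 mg (22 v 8). For 2 mg, an illustrative 18/22 v 4/8 gives 32 points, 95% CI −3 to 62. A within-dose contrast is too imprecise to lead, above all for 2 mg.

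**The case against.** **Description was a deliberate choice.** SAP 4.1 says the withdrawal was not sized to detect a difference, the objective is outside multiplicity control, and 4.2.3 separately rules out tests at the final lock. These are fair reasons not to make a confirmatory claim. They are not the reason given in 4.11.5, and none of them argues against an estimate with a nominal interval. An unsized comparison has all the more need to show its uncertainty.

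**The SAP leaves room for a contrast.** Both restrictions allow for exceptions stated elsewhere, and 4.2.3 has log-rank and Cox text. This stands as far as it goes: the SAP is inconsistent rather than silent. But no table states the exception. SAP 4.11.5 still defers detail to a future version, although Version 5 was written for the final lock.

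**The evidence is not lost.** Correct. Counts and curves by arm are planned, so a reader could compute a difference. What is missing is the pre-specified contrast.

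**Other sources may fill the gap.** The main protocol JAHO(e) and the supplemental SAP mentioned in 4.18 were not supplied. The protocol supplied is the open-label addendum, which has no withdrawal. This point rests on the SAP alone.

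**Stronger readings that the documents do not support.**
- *That the SAP merges former 2-mg and 4-mg patients into one placebo arm.* Table JAHO.4.1 can be read that way, but no table layout says so. SAP 3.2 says the withdrawal randomisation was not stratified. Pooling both doses on both sides would still be a randomised comparison; setting 4-mg stayers against all placebo patients would mix doses. The SAP needs to state its grouping.
- *That a log-rank test would be well powered and should be required.* That needs an event count and a hazard ratio, and the documents give neither. The 80% v 52% illustration implies 15 + 12 = 27 events before censoring and a hazard ratio near ln 0.80/ln 0.52 = 0.34. Schoenfeld power is then Φ(1.075 × √(27 × 0.75 × 0.25) − 1.96) = Φ(0.46), about 68%.

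**Conclusion.** The concern holds as a gap in the analysis plan and an error in its rationale. The reason in 4.11.5 is incorrect for the Randomized Withdrawal Population, no table supplies a between-arm estimate with its uncertainty, and the log-rank and no-test statements within 4.2.3 are not reconciled.

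A pooled contrast on about 75 v 25 would have an interval roughly 40 points wide. It could be clear of zero (28 points, 7 to 48) or barely so (20 points, 0.4 to 41). These figures rest on assumed maintenance rates and on the SAP's expected 100 patients. The case for reporting an interval does not depend on power.

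The change is worth making but is not critical. The objective is other secondary, and the primary and key secondary conclusions are unaffected.

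**What to change.** 1. Correct the sentence in SAP 4.11.5 so that the lack of placebo control is not given as the reason for the withdrawal population.
2. For that population, by Week 52 randomised arm, add the difference in proportions with 95% Newcombe-Wilson interval at each planned visit, and a Cox hazard ratio with 95% interval for time to loss of benefit. Label both nominal and outside the alpha-controlled family. No significance test is needed.
3. Lead with a pooled estimate stratified by pre-withdrawal dose. Give the within-dose contrasts as supportive, and say that they will be imprecise.
4. State how patients moved to placebo from 2 mg and from 4 mg are grouped in each display.
5. Reconcile the log-rank and Cox text in 4.2.3 with the final-lock rule in the same section.
6. If the contrasts are specified after the Week 104 and Week 152 locks (SAP 4.17.3.3 and 4.17.3.4), say so in the SAP and the report. A nominal label alone does not disclose that timing.

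If the sponsor prefers description only, the alternative is to justify it on sizing and reword the Table JAHO.2.1 objective to match.

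The cost is SAP wording and a few table rows, with no new data. The drawback is that the intervals are unadjusted and possibly specified after interim results were seen, and must be presented as such.

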**Table JAHO.4.8. Description of Analysis Beyond Week 36 Placebo-Controlled Period**

Measure	Variable	Analysis Method (Section 4.2.3)	Population (Section 4.2.1)	Comparison/Time Point	Analysis Type
Severity of Alopecia Tool (SALT)	Proportion of patients maintaining SALT $\leq 20$	Descriptive	Randomized Withdrawal Population	Summary statistics will be provided at each post-baseline visit during the Long-Term Extension and Bridging Long-Term Extension Period	Other Secondary
	Proportion of patients with >20-point absolute worsening in SALT score	Descriptive	Randomized Withdrawal Population	Summary statistics will be provided at each post-baseline visit during the Long-Term Extension and Bridging Long-Term Extension Period	Other Secondary
	Time to >20-point absolute worsening in SALT score	Kaplan-Meier Plot	Randomized Withdrawal Population	Summary statistics will be provided at each post-baseline visit during the Long-Term extension and Bridging Long-Term Extension Period.	Other secondary
	Proportion of patients achieving SALT $\leq 20$	Descriptive	Retreated Population	Summary statistics will be provided at Weeks 12, 16, 24, and 36 of retreatment with baricitinib	Other secondary
	Percent change in SALT score	Descriptive	Retreated Population	Summary statistics will be provided at Weeks 12, 16, 24, and 36 of retreatment with baricitinib	Other secondary
PRO for Scalp Hair Assessment	Proportion of patients with a PRO for Scalp Hair Assessment score of 0 or 1	Descriptive	Retreated Population	Summary statistics will be provided at Weeks 12, 16, 24, and 36 weeks of retreatment with baricitinib	Other secondary

